#### 4. TREATMENT PLAN

Subjects will be assessed for eligibility and enrolled prior to allogeneic HCT, using the pre-transplant inclusion and exclusion criteria above. Eligible and enrolled subjects will then be reassessed prior to the administration of ibrutinib, which may begin at any point between Day +60 and Day +90 after allogeneic HCT, using the pre-ibrutinib inclusion and exclusion criteria above. Ibrutinib will not be initiated until the enrollment checklist has been reviewed by the coordinating center; a minimum of 48 hours' notice is required.

If subjects are deemed ineligible prior to beginning ibrutinib therapy, they may be reassessed for eligibility at any point until Day +90 after allogeneic HCT, and ibrutinib may be initiated if they meet all relevant criteria at any point between Day +60 and Day +90 after allogeneic HCT. Subjects beyond Day +90 will not be eligible to initiate ibrutinib if they have not already done so.

**Pre-transplant screening: all studies to be completed within 60 days of beginning conditioning therapy, unless otherwise indicated:**

- History and physical examination, including Karnofsky Performance Status (**standard of care**)
- Serologic and/or nucleic-acid testing for HIV, hepatitis B, and hepatitis C according to institutional standard practice (**standard of care**)
- Serum pregnancy testing, for women of childbearing potential (**standard of care**)
- Bone marrow examination, including assessment of minimal residual disease by multiparameter flow cytometry or high-throughput sequencing (**standard of care**)
- Disease assessment (**standard of care**): Data forms for CIBMTR will be made available to the coordinating center. Alternatively, detailed disease assessment data will be entered directly into the electronic database.
- Complete enrollment checklist and submit to coordinating center for review prior to enrollment. Preparative regimen for HCT should not begin until enrollment checklist has been reviewed by coordinating center (**research**).

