## **12. STATISTICAL CONSIDERATIONS**

### **12.1 Statistical Design, Effect Size, and Sample Size**

This study is designed as a single-arm efficacy trial using historical published controls. This study's primary endpoint is the incidence of relapse at 18 months after allogeneic HCT for AML/ALL. Baseline relapse rates after reduced-intensity conditioning for these diseases in the published literature vary from 40–60% (1-6). For the purposes of study design, we will use a relatively conservative baseline relapse risk of 45%. This study is designed to detect a decrease in relapse rate from 45% to 25%. Therefore, in the power analysis we will assume that the true relapse rate in the study population is 25%, while the null hypothesis holds that the relapse rate is 45%. Under these conditions, using intent-to-treat analysis, a sample size of 50 enrolled subjects will provide 84% power to conclude that the relapse rate is lower than 45% at the two-sided significance level of 0.05. Conservatively assuming that 45 of these 50 subjects meet the secondary criteria to continue to ibrutinib treatment (Appendix B) and are treated with ibrutinib, a subgroup analysis restricted to these 45 subjects will have 78% power to conclude that the relapse rate is < 45% with a significance level of 0.05.

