## 12.2 Interim analyses

We will monitor major adverse event rates as described above, in particular serious bleeding complications (hemorrhage Grade 3 or 4, as defined by CTCAE v4.0). We will monitor and estimate the incidence rate of serious bleeding in study participants, and report all occurrences and corresponding analytic summaries (such as the estimated incidence rate with 95% confidence intervals) to the DSMB to assist in decision-making regarding early termination for safety.

Allogeneic HCT is an intensive therapy with many associated side effects and toxicities related to the transplant conditioning regimen; the ensuing immunosuppressed status; adverse effects of standard post-transplant medications; and graft-vs-host interactions or GvHD. Toxicities, including Grade 4 toxicities, are relatively common. Non-relapse mortality (NRM) is a definitive endpoint which captures fatal effects of any aspect of the transplant process outside of disease relapse, and thus represents the most accurate and reproducible measure of the toxicity and safety of the allogeneic HCT process.

The baseline cumulative incidence of NRM after allogeneic HCT for acute leukemia with FLU/MEL conditioning was estimated in a recent large cohort study at 20% (22). In order to ensure that patients are not harmed by the study intervention, the formal stopping rule below monitors that the study intervention does not increase the risk of NRM in participants.

The stopping rule is based on the incidence of NRM at 1 year after allogeneic HCT. Patients will be evaluable with regard to the stopping rule if they die or if they reach 1 year post-transplant, whichever occurs first. The stopping rule will be tested every increment of 5 evaluable patients. The stopping rule will be triggered if any of the following conditions are met:

Number of evaluable patients	Number of patients with NRM
5	3
10	5
15	6
20	8
25	9
30	10
35	12
40	13

If the stopping rule is triggered, the study will be terminated, and FDA so notified. This stopping rule provides 80% power to detect an increase in NRM with a type I error rate of 0.05. The stopping rule was constructed using the Pocock boundary with the same significance level for all looks at the data. The rule was created using R v.3.1.3 and the clinfun package.

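### Section 12.1 calls 45 treated of 50 enrolled a conservative assumption without deriving it; at the plan's own baseline rates it is optimistic, and the target size is stated in three ways

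*Combined protocol and SAP*

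**What the plan says.** Section 12.1 sets the primary test at 45% versus 25% relapse at 18 months, "at the two-sided significance level of 0.05", with 84% power from 50 enrolled subjects. It then turns to the treated subjects: "Conservatively assuming that 45 of these 50 subjects meet the secondary criteria to continue to ibrutinib treatment (Appendix B) and are treated with ibrutinib", it states that "a subgroup analysis restricted to these 45 subjects will have 78% power". No derivation of the 45 is given.

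Enrolment is before transplant (Section 4). Ibrutinib may start from Day +60, and "Subjects beyond Day +90 will not be eligible to initiate ibrutinib if they have not already done so". Relapse after transplant bars treatment (Section 3.2.2), as do the other items in Appendix B, which lists 7 continuation and 19 withdrawal criteria.

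On background rates, Section 12.1 adopts 45% relapse and notes that rates in the "published literature vary from 40–60% (1-6"). Section 12.2 says that baseline NRM "with FLU/MEL conditioning was estimated in a recent large cohort study at 20% (22"), and its stopping rule uses NRM at 1 year. Section 7.2 puts NRM after reduced-intensity conditioning at about 10% with a sibling donor and 20% with an unrelated donor.

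The target size appears three times. The Synopsis gives 50 subjects as both enrolled and treated. Section 12.1 has 50 enrolled with 45 treated. Section 12.3 has an accrual goal of 45 toward which untreated subjects do not count.

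**The concern.** A 10% allowance has to cover every loss between pre-transplant enrolment and the first dose: death, relapse and failure of any Appendix B criterion. A conservative figure should sit below the expected number treated. If relapse and death alone use up about 10% or more, 45 sits at or above expectation, and the stated power of the treated-subset analysis describes a sample that 50 enrolments probably do not supply. The enrolment needed would then exceed 50, and the three size statements leave unclear whether the plan intends that.

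**Working it through.** **1. The plan's own figures.** Exact one-sample binomial, null 0.45, alternative 0.25, lower-tail error at most 0.025:

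- n = 50: reject at 15 or fewer relapses; error 0.0220; power 83.7% (stated 84%).
- n = 45: reject at 13 or fewer; error 0.0201; power 78.4% (stated 78%).

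Both reproduce. There is no arithmetic error.

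**2. Subjects able to start.** Inputs from the documents: relapse 45% at 18 months (12.1), which is the relevant rate before any drug is given; NRM 20% (12.2), taken at the stopping rule's 1 year. Timing is not given, so constant cause-specific hazards are assumed. With *a* for relapse, *b* for NRM, *h* = *a* + *b*, time in years:

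- (a/h)(1 − exp(−1.5h)) = 0.45 and (b/h)(1 − exp(−h)) = 0.20 give a = 0.518, b = 0.292, h = 0.810.
- Alive and relapse-free at day d: S(d) = exp(−0.810 × d/365.25).

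| | Day +60 | Day +75 | Day +90 |
|---|---|---|---|
| S(d) | 0.875 | 0.847 | 0.819 |
| Expected of 50 | 43.8 | 42.3 | 41.0 |
| Probability of 45 or more | 0.40 | 0.20 | 0.09 |

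So 12% to 18% are lost before any other criterion applies.

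**3. Milder assumptions, still at 45% relapse.** Constant hazards, Day +60: 44.6 with 20% NRM by 18 months; 45.2 with 15% by 18 months; 45.4 with 10% by 1 year; 45.8 with 10% by 18 months. A linear spread at 20% NRM by 1 year gives 50 × (1 − 0.45 × 60/547.9 − 0.20 × 60/365.25) = 45.9 at Day +60. The most favourable case, linear with 10% NRM by 18 months, gives 50 × (1 − 0.45 × 60/547.9 − 0.10 × 60/547.9) = 47.0.

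**4. Appendix B losses.** The documents give no failure rate. If 5% fail (assumption), the most favourable case becomes 47.0 × 0.95, about 44.6, so every case above is below 45. At 20% NRM by 1 year the counts become 41.6, 40.2 and 38.9 at Day +60, +75 and +90; with 10% failing, 39.4, 38.1 and 36.9.

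**5. Power by number treated**, taking 25% as the relapse rate among treated subjects, as the 78% does:

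| Treated | 37 | 38 | 39 | 40 | 41 | 42 | 43 | 44 | 45 |
|---|---|---|---|---|---|---|---|---|---|
| Exact power, % | 69.1 | 65.6 | 74.7 | 71.5 | 68.2 | 76.6 | 73.7 | 70.6 | 78.4 |

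Power moves in steps, so no single value of n should be singled out. Averaged over a binomial number treated from 50, at 20% NRM (by 1 year or by 18 months) and no Appendix B failures, it is about 72% to 76%.

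**6. Enrolment needed for 45 treated** at 45% relapse and 20% NRM by 1 year: 45/0.875, 45/0.847 and 45/0.819 round up to 52, 54 and 55. Dividing again by 0.90, for a further 10% ineligible, gives 58, 60 and 62.

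**The case against.** Four points can be made for the plan.

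First, 45 is within reach. Ibrutinib may start at Day +60, the 20% NRM figure is for FLU/MEL while FLU/BU is also allowed, and sibling-donor NRM is about 10%. This stands. A reader might infer that 45 is a best case, or is reached only with 10% NRM. The documents do not support that, because steps 3 and 4 show counts of 45 to 47 before Appendix B losses, and neither event timing nor Appendix B failure rates are given.

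Second, Section 12.3 can be read as accruing until 45 are treated, which delivers n = 45 and 78% whatever the attrition. This also stands, but enrolment is then above the 50 given in 12.1 and the Synopsis.

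Third, Section 12.1 says that "in the power analysis we will assume that the true relapse rate in the study population is 25"% and applies this to all enrolled. If 9.8% relapse by Day +75 and 84.7% start, a 25% rate overall implies (0.25 − 0.098)/0.847, about 18%, among the treated. Exact power is then about 97% at 42 treated and 93% at 38. The null moves too: (0.45 − 0.098)/0.847 is about 41.6%, and at n = 45 the lower-tail error of the 13-or-fewer rule rises from 0.020 to about 0.055. A reader might therefore take 66% to 77% as the true power. It is not: it holds only if 25% is the rate among treated subjects. That is also the condition behind the plan's 78%, and the plan should say so.

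Fourth, this is a planned subset analysis. A reader might infer that the trial is underpowered for its primary aim. The 84% does not use the treated count, so nothing here shows that.

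**Conclusion.** The point holds as a matter of planning assumptions, not arithmetic. Calling 45 of 50 conservative is unsupported. At 45% relapse and 20% NRM by 1 year with constant hazards, about 41 to 44 can start, and a modest assumed 5% Appendix B loss takes every 45%-relapse case checked below 45. For 42 to 44 treated, the fall in exact power from 78.4% is about 2 to 8 points (76.6% to 70.6%). Over 37 to 44 treated it is about 2 to 13 points, given 25% relapse among treated subjects. Separately, and without any modelling, the Synopsis, 12.1 and 12.3 do not agree on how many subjects are to be enrolled and how many treated.

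**What to change.** In Section 12.1:

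- Delete *Conservatively*.
- State the assumed losses before the first dose from early relapse, NRM and Appendix B failure, with their timing.
- Replace the single 78% by exact power over about 37 to 45 treated, and say that 25% is assumed to be the relapse rate among treated subjects.

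Across the Synopsis, 12.1 and 12.3, state one accrual rule. If accrual stops at 50 enrolled, remove the goal of 45 treated from 12.3 and the claim of 50 treated from the Synopsis. If accrual runs until 45 are treated, replace 50 by the enrolment this implies: about 52 to 55 from relapse and death alone at 45% and 20%, and up to about 62 with a further 10% ineligible.

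The cost is a few sentences and a slightly less favourable power for a secondary analysis. The restatement itself needs no extra patients; enrolling beyond 50 would follow only from choosing the 45-treated rule.

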## 1. OBJECTIVES

### 1.1 Primary Objective

- To reduce the incidence of relapse at 18 months after RIC and allogeneic HCT for AML, ALL, and CML in blast crisis from a historical baseline of 45% to 25%, using ibrutinib maintenance therapy.

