#### **3.2.2 Exclusion Criteria (prior to ibrutinib administration)**

- Active and uncontrolled acute GvHD Grades III or IV
- Use of secondary therapy for acute GvHD at any time (defined as any systemic therapy intended to treat acute GvHD besides corticosteroids)
- Requirement for anticoagulation with warfarin or other Vitamin K antagonists (concomitant use of other anticoagulants is permitted)
- Relapsed leukemia (> 5% leukemic blasts in peripheral blood or bone marrow after allogeneic HCT)
- Karnofsky Performance Status < 60%
- Chemotherapy  $\leq$  21 days prior to first administration of study treatment and/or monoclonal antibody  $\leq$  6 weeks prior to first administration of study treatment
- Vaccinated with live, attenuated vaccines within 4 weeks of first dose of study drug.
- Currently active, clinically significant cardiovascular disease, such as uncontrolled arrhythmia or Class 3 or 4 congestive heart failure as defined by the New York Heart Association Functional Classification; or a history of myocardial infarction, unstable angina, or acute coronary syndrome within 6 months prior to randomization.

- History of stroke or intracranial hemorrhage within 6 months prior to screening
- Any life-threatening illness, medical condition, or organ system dysfunction that, in the investigator's opinion, could compromise the subject's safety or put the study outcomes at undue risk.
- Major surgery within 4 weeks of first dose of study drug.
- Any uncontrolled active systemic infection.
- Unresolved toxicities from prior anti-cancer therapy, defined as having not resolved to Common Terminology Criteria for Adverse Event (CTCAE, version 4), Grade ≤ 1, or to the levels dictated in the inclusion/exclusion criteria with the exception of alopecia
- Unable to swallow capsules or malabsorption syndrome, disease significantly affecting gastrointestinal function, or resection of the stomach or small bowel, symptomatic inflammatory bowel disease or ulcerative colitis, or partial or complete bowel obstruction
- Requires treatment with a strong cytochrome P450 (CYP) 3A4/5 inhibitor (see Appendix E).
- Unwilling or unable to participate in all required study evaluations and procedures.
- Unable to understand the purpose and risks of the study and to provide a signed and dated informed consent form (ICF) and authorization to use protected health information (in accordance with national and local subject privacy regulations).

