### **12.3 Analysis Population**

Subjects who are enrolled but never treated with ibrutinib (eg, due to failure to meet the secondary criteria to continue to ibrutinib treatment) will be included in the primary analysis, which will be performed as an intention-to-treat analysis. However, they will not be counted toward the overall accrual goal of 45 subjects. A planned subset analysis will be performed testing the primary and secondary endpoints in the subset of subjects who receive at least 1 dose of ibrutinib on study.

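### The treated-subset test uses a 45% null counted from transplant for subjects selected as relapse-free at Day +60 to +90, so rejecting 45% does not by itself show a drug effect

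*Combined protocol and SAP*

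**What the plan says.** The time origin of the benchmark is transplant. The primary objective (section 1.1) reads "To reduce the incidence of relapse at 18 months after RIC and allogeneic HCT for AML, ALL, and CML in blast crisis from a historical"; the sentence then sets the starting rate at 45% and the target at 25%. Section 12.1 gives the source range, "Baseline relapse rates after reduced-intensity conditioning for these diseases in the published literature vary from 40–60% (1-6"), and the design assumption: "we will assume that the true relapse rate in the study population is 25%, while the null hypothesis holds that the relapse rate is 45" per cent.

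Two power figures follow in section 12.1, both against the same 45%. For all enrolled subjects, "a sample size of 50 enrolled subjects will provide 84% power". The level attached to that figure is given as "84% power to conclude that the relapse rate is lower than 45% at the two-sided significance level of 0.05". The plan then assumes that 45 of the 50 go on to ibrutinib, and "a subgroup analysis restricted to these 45 subjects will have 78% power to conclude that the relapse rate is < 45" per cent, at a significance level of 0.05 whose sidedness is not restated.

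Section 12.3 confirms that this is to be a test among subjects given ibrutinib: "A planned subset analysis will be performed testing the primary and secondary endpoints in the subset of subjects who receive at least 1 dose".

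Entry to the subset is decided later than transplant. Sections 3 and 4 place the second eligibility check and the start of ibrutinib between Day +60 and Day +90, and section 3.2.2 excludes "Relapsed leukemia (> 5% leukemic blasts in peripheral blood or bone marrow after allogeneic HCT"). Appendix B has the same criterion. Section 4 also schedules a marrow examination between Day +28 and Day +60, so early relapses are looked for before the drug can start.

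The documents give no landmark or conditional null for the subset, and no rate of relapse or death before Day +60 to +90.

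**The concern.** A relapse rate counted from transplant includes relapses in the first two to three months. The treated subset cannot contain them. It also cannot contain subjects who die in that period, and those deaths sit in the denominator of the from-transplant rate. With no drug effect, the 18-month relapse rate in the subset is therefore not necessarily 45%. It may be lower or higher, depending on who drops out before the start of ibrutinib.

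This is a landmark population compared with a benchmark that has no landmark. If early relapse is the main reason for not starting, the test can reject 45% through selection alone. The result describes the subjects actually exposed to ibrutinib and carries its own power statement, so it could easily be read as evidence of efficacy.

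**Working it through.** **Inputs.** From section 12.1: null 45%, alternative 25%, 50 enrolled, 45 treated, two-sided 0.05 (2.5% in the lower tail). From section 12.2: non-relapse mortality (NRM) of 20%, quoted for FLU/MEL and without a time horizon. Not in the documents: the share of enrolled subjects who relapse before starting (e) and the share who die without relapse before starting (m). These are varied below.

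**Step 1: reproduce the plan's figures.** Exact one-sample binomial test, lower tail at most 2.5%.
- n = 50: reject at 15 or fewer relapses. P(X ≤ 15 | 0.45) = 2.2%; power P(X ≤ 15 | 0.25) = 83.7%. The plan says 84%.
- n = 45: reject at 13 or fewer. P(X ≤ 13 | 0.45) = 2.0%; power P(X ≤ 13 | 0.25) = 78.4%. The plan says 78%.

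A one-sided 0.05 test with n = 45 would reject at 14 or fewer and have 86.7% power. The stated 78% therefore fits a two-sided test.

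**Step 2: the null that fits the subset.** With no drug effect, and with any other reason for not starting unrelated to relapse risk, the subset's relapse rate is

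(0.45 − e) / (1 − e − m).

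Let the plan's own 10% loss (5 of 50) consist only of early relapses and early non-relapse deaths. Of 50 × 0.45 = 22.5 expected relapses, k occur before the start, so the subset null is (22.5 − k)/45. The error is P(X ≤ 13 | 45, that null).

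| Early relapses k | Early deaths | Subset null | Lower-tail error |
|---|---|---|---|
| 0 | 5 | 50.0% | 0.3% |
| 1 | 4 | 47.8% | 0.8% |
| 2 | 3 | 45.6% | 1.7% |
| 3 | 2 | 43.3% | 3.4% |
| 4 | 1 | 41.1% | 6.3% |
| 5 | 0 | 38.9% | 10.9% |

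With an even split (e = m = 5%) the null is 0.40/0.90 = 44.4% and the error is 2.4%. If instead the five non-starters are alive with average relapse risk (e = m = 0), the null stays at 45% and the error at 2.0%.

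**Step 3: one scenario with both early events.** Assume constant hazards, 45% relapse and 20% NRM, both at 18 months. Event-free at 18 months is 1 − 0.65 = 35%, so the cumulative hazard is −ln 0.35 = 1.050. For a start at day d, with f = d/547.5, the subset null is (45/65) × [1 − exp(−1.050 × (1 − f))].

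| Start | Subset null | Error | Error ÷ 2.5% |
|---|---|---|---|
| Day 60 | 42.1% | 4.9% | 1.95 |
| Day 75 | 41.3% | 6.1% | 2.4 |
| Day 90 | 40.4% | 7.5% | 3.0 |

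**Step 4: power against a corrected null.** The cut-off is reset for each row of the Step 2 table so that the tail stays within 2.5%. Power at a true 25% then runs from 92% (no early relapses) to 41% (five). If the 25% is conditioned in the same way, as (12.5 − k)/45, power runs from 84% to 88%. Power can therefore move either way, depending on which alternative is meant.

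**The case against.** The case against has several sound parts.

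- A reader might infer that the 78% is miscalculated. It is not. It reproduces exactly as power to conclude that a rate is below 45% when it is 25%, and the rule keeps its level for that literal hypothesis.
- A reader might infer that the 0.05 level fails whatever happens before Day +90. The documents do not support that. With zero, one or two early relapses among the five non-starters, the error is within 2.5%. Early deaths push the null up, and an even split roughly keeps the level. Without early relapse or death rates, neither the direction nor the size can be fixed.
- Not every non-starter has relapsed or died. Sections 3.1.2 and 3.2.2 also exclude living subjects, for example for blood counts, organ function, GvHD or infection. If their relapse risk is average, the null does not move.
- The constant-hazard scenario is an assumption. The 20% NRM has no stated horizon. The hazards also imply losses of 10.9%, 13.4% and 15.8% by Day 60, 75 and 90, which already exceed the plan's 10%, while the calculation keeps n = 45.
- The 45% is itself chosen from a 40–60% range. With a 50% baseline, 10% early relapse and no early deaths, the subset null is 0.40/0.90 = 44.4% and the error 2.4%.

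These points limit what can be said about size. They do not supply a null suited to the subset. The level would be kept only if early losses happened to balance, or if non-starters had average relapse risk, and the plan neither states nor justifies either. The baseline range does not help either, because the plan tests against 45% and not against a range.

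**Conclusion.** The mismatch is established from the documents: a from-transplant 45% is applied without adjustment to subjects who must be alive and relapse-free at Day +60 to +90. Rejecting it in that subset does not by itself show a drug effect.

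The error rate against the no-drug-effect rate is not assured. It lies between 0.3% and 10.9% over the Step 2 splits of the plan's own five non-starters, and exceeds 2.5% once three of them are early relapses. Under the constant-hazard assumption it is about two to three times the nominal 2.5% per tail. Inflation is plausible when early relapse dominates, but the documents do not show that it does.

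A reader might extend the problem to the main result. That would be wrong: the primary analysis counts all enrolled subjects from transplant, including those never treated, so it does not have this mismatch.

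**What to change.** In sections 12.1 and 12.3, remove the test of the treated subset against 45%, and its 78% power claim, as evidence of efficacy. Report the subset descriptively as supportive: its relapse rate with a confidence interval, and a note that subjects were selected at Day +60 to +90. Listing the non-starters by reason (relapse, death without relapse, other ineligibility) would let readers judge the direction of the selection.

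If a test is kept, take the null from historical patients alive and relapse-free at a Day +60 to +90 landmark. State whether the alternative is conditioned in the same way, and restate the power and sidedness for that null.

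The cost is a change of wording and one secondary power figure lost or restated. A retained test would also need suitable historical landmark data. The primary analysis, sample size and visits stay as they are.
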